Virtual Diabetes Specialty Clinic: A Study Evaluating Remote Initiation of Continuous Glucose Monitoring

VDiSC Study

Statistical Analysis Plan

Version: 1.0

Version Date: 12/30/2020

Author: [name]

Based on Protocol Version: 2.0

Note: The table shells are included in a separate document.

Revision History

The following table outlines changes made to the Statistical Analysis Plan.

Version Number	Author	Approver	Effective Date	Study Stage
1.0	[name]	[name]	12/30/2020	Study Enrollment

Version Number	Revision Description

Approvals

Role	Digital Signature or Handwritten Signature/Date
Author: [name]	
Senior Statistician: [name]	
JCHR Sponsor Representative: [name]	

1 **1 Statistical and Analytical Plans**

2 This document summarizes the proposed analyses to be performed for the Virtual Diabetes
3 Specialty Clinic (VDiSC) study. All analyses are exploratory and additional analyses and
4 outcomes not pre-specified here may be performed in the future. The table shells detailing how
5 the results will be displayed will be shown in a separate document.

6

7 **2 Study Overview**

8

9 The following two tables gives an overview of the VDiSC study.

10 **Table 1. Study Overview**

PARTICIPANT AREA	DESCRIPTION
Title	Virtual Diabetes Specialty Clinic: A Study Evaluating Remote Initiation of Continuous Glucose Monitoring
Précis	This study will assess feasibility and efficacy of establishing a virtual diabetes clinic with a focus on introduction of CGM technology and ongoing CGM use to minimize such rate-limiting factors as geography, cost and access to specialty care
Objectives	The objective of this study is to evaluate a virtual diabetes clinic model, for adults with either T1D or T2D, that supports integration of CGM into diabetes self-management and use of decision support technology.
Study Design	Single-arm prospective longitudinal study

PARTICIPANT AREA	DESCRIPTION
Eligibility Criteria	
Inclusion Criteria
 
 • Age ≥ 18 years old • Diagnosis of type 1 diabetes or type 2 diabetes and using insulin therapy (at least 3 injections of insulin per day or insulin pump that is compatible with Tidepool software) Multiple daily injection (MDI) users must be willing to use a device provided by the study that records the injection dosages and/or enter insulin dosing information through an app • See a healthcare provider at least once a year • Resident of United States and plan to reside in the U.S. for the duration of the study This requirement is due to virtual clinic license requirements and U.S. use restrictions for some study software and devices. Not all U.S. states may be eligible for inclusion due to virtual clinic license status. • Use either an Android or iOS smartphone that is compatible with app requirements that are needed for the study • Access to a compatible computer with internet • Understand written and spoken English • Willing and able to follow the study procedures as instructed 
Exclusion Criteria
 
 • Use of real-time CGM (including Abbott Libre or integrated pump system) in last 12 months (interval blinded CGM use is acceptable) • Current use of any off-label glucose-lowering medications for diabetes type (Example: T1D use of non-insulin, anti-diabetic medications including SGLT2 inhibitors) Use of such medications during the study will also be prohibited. • Females who are pregnant, intending to become pregnant, or breastfeeding during the study • Current renal dialysis or plan to begin renal dialysis during the study • Active cancer treatment • Extreme visual or hearing impairment that would impair ability to use real-time CGM • Known adhesive allergy/prior skin reaction or skin reaction identified during the blinded CGM use phase that would preclude continued CGM use • Participation in a different diabetes management study during the study • Planned relocation to a state other than current state of residence during the study if virtual clinic is not licensed in the new state. Individuals working routinely in a state other than current state of residence in the next six months are also ineligible if the virtual clinic is not licensed in that state.
Sample Size	The recruitment target is 300 initiating CGM.
Outcomes	
Efficacy Outcomes: CGM use; CGM metrics for hypoglycemia (<54 and <70 mg/dL), hyperglycemia (>180 and >250 mg/dL), time in range (70-180 mg/dL), mean glucose, and glycemic variability (coefficient of variation); HbA1c; participant- reported outcomes including psychosocial and diabetes treatment satisfaction questionnaires
 
Safety Outcomes: Severe hypoglycemia, diabetic ketoacidosis, hospitalizations, and emergency room visits

Participant Duration	Study participation will be up to 12 months.
Protocol Overview/Synopsis	
Patient Population Adults ≥ 18 years with type 1 diabetes or type 2 diabetes using insulin therapy who are not CGM users will be enrolled. Potential participants

PARTICIPANT AREA	DESCRIPTION
	
may be recruited through insurance providers, primary care networks, or health care providers.
 
Baseline Data Collection Baseline data collected will include demographics, height and weight, socioeconomic status, diabetes history, knowledge of and experience with diabetes devices, medical history and medications, and health-related physical activity. Questionnaires will collect information related to hypoglycemia awareness, treatment satisfaction, and psychosocial issues. Participant contact information will be collected. Contact information for the participant's diabetes healthcare provider will also be collected.
 
HbA1c Participant will receive fingerstick HbA1c kits that will be sent to a central lab for measurement after enrollment and at 13 weeks, 26 weeks, 39 weeks, and 52 weeks.
 
Contact between Study Team and Participant Each participant will be assigned to work with virtual clinic team members. Mental health service support options for diabetes-related mental health issues will be discussed as needed.
 
Virtual clinic team members will check in with participants during study follow up to review CGM data and recommendations related to diabetes management.
 
CGM Use Participants will use a blinded CGM device for a single sensor wear period prior to CGM initiation. Participants may be asked to use a blinded CGM for an additional sensor wear period(s) if enough CGM data are not available to establish a baseline that can be used as baseline comparator data. Virtual training will include CGM set up, sensor insertion, alerts and alarms, uploading data, and visualizing data.
 
Changes in Insulin Dosing If the virtual clinic team believes that changes in insulin type or dosing should be considered, they will work with the participant to implement any such changes. Decision support tools, which include use of a mobile application, may be used if available to provide the virtual clinic team with potential recommendations regarding insulin use.

Table 2. Schedule of Visits and Procedures

				Virtual Clinic Training Phase (0-13 Weeks)					Extended Virtual Clinic Follow Up Phase	Optional Participant Follow Up
	Enrollment	Initial Virtual Clinic Contact	Baseline CGM Data Collection	Training 1 (Week 0)	Training 2 (Week 1)	Training 3 (Week 3)	CGM Follow Up (Weeks 4, 8)	CGM Follow Up (Week 13)	Follow up (>13-26 Weeks)	Follow Up (>26-52 Weeks)
TARGET WINDOW		Within 7 Days from Completion of Enrollment Questionnaires		Day 0	Day 7-14	Day 21-28		Weeks 12-14		
ICF • Eligibility Confirmation	X								X*	X*
Baseline Data Collection • Contact Information • Demographics • Medical History • Questionnaires	X		X							
Follow-Up Data Collection**					X	X	X	X	X	X
HbA1c***			X					X	X	X
Video Tutorials / Access to Resource Materials		Examples: CGM Overview Parts of CGM	Examples: HbA1c Sample Collection CGM Setup	Examples: Understanding Your Real-Time Data How to Change Sensor	Examples: How to Upload CGM Data How to View Reports Understanding Your Ambulatory Glucose Profile / Data Patterns	X	X	X	X	
Contact with Study Team [†]		X	X	CGM Initiation	CGM Data Interpretation	CGM Data Review Goal Setting	X	X	X	
CGM Use ^{††}			~2 Week Blinded CGM Use	Start of 26-Week Unblinded CGM Use	X	X	X	X	X	

*Virtual Clinic Training and Follow up phase ends at 26 weeks. Participant will be asked to extend follow up for an additional 26 weeks and sign an addendum ICF if they plan to continue to use CGM after the first 26 weeks.
 **Participants will be asked to complete questionnaires monthly after CGM Initiation. A final questionnaire will be elicited at the earlier of CGM discontinuation or completion of study follow up (~52 weeks).
 ***HbA1c checks prior to unblinded CGM initiation, and at 3-month intervals following CGM initiation (~13 weeks, 26 weeks, 39 weeks, and 52 weeks)
[†]Follow up may be via phone, text, virtual (i.e. Skype), or app. outside of scheduled training. Additional follow up may be conducted as needed. Participants may follow up with study team as needed.
^{††}CGM supplied for blinded data collection will be provided. CGM supplies for six months of unblinded use will be provided for those who successfully complete blinded data collection.

3 Statistical Hypotheses

There are no primary outcomes and additional analyses not pre-specified here may be performed. In this study, we expect that most hypothesis testing will involve testing whether the change from baseline for various outcomes is significantly different from zero. This will primarily be for the CGM metrics, HbA1c, and the questionnaires. In those cases, the null hypothesis of the change from baseline being equal to zero will be tested against the alternative hypothesis that the change from baseline is nonzero. Analyses will be stratified by type of diabetes.

4 Sample Size

The goal for the study is to include at least 300 participants who initiate CGM. This is a convenience sample and not based on statistical principles.

5 Outcome Measures

The following quantitative study outcome measures will be tabulated by diabetes type using summary statistics appropriate to the distribution:

- HbA1c
- Percentage of time using the CGM
- Hours of CGM use
- Mean of sensor glucose levels
- Percentage of time spent with sensor glucose levels <54 and <70 mg/dL
- Percentage of time spent with sensor glucose levels >180 and >250 mg/dL
- Percentage of time spent with sensor glucose levels in the target range (70-180 mg/dL)
- Glycemic variability measured by the coefficient of variation
- Total daily insulin (units/kg)
- Total daily basal insulin (units/kg)
- Total daily bolus insulin (units/kg)
- Patient Health Questionnaire-8
- Diabetes Distress Scale Management Distress Subscale
- Hypoglycemia Fear Survey Worry Subscale
- CDC Healthy Days
- Hypoglycemia Confidence Survey
- Diabetes Technology Attitudes Survey
- Glucose Monitoring Satisfaction Survey
 - Openness Subscale
 - Emotional Burden Subscale
 - Behavioral Burden Subscale
 - Trust Subscale
- Sleep Quality Scale
- Benefits and Barriers of CGM Survey
- Percentage of CGM discontinuations
- CGM Discontinuation Survey (only administered to subjects who discontinue CGM)
- Positive screen for mental health

41 ○ Positive screen triggered by Patient Health Questionnaire-8
 42 ○ Positive screen triggered by Diabetes Distress Scale
 43 ○ Positive screen triggered by Hypoglycemic Fear Survey Worry Scale
 44 • Behavioral health service utilization
 45 • Behavioral health metrics
 46 • Cost of care over time
 47 • Service utilization such as hospitalizations, ER visits, prescriptions filled

48
 49 CGM, HbA1c, and insulin outcomes will be evaluated at baseline and 13, 26, 39, and 52 weeks.
 50 CGM and insulin outcomes will also be evaluated over the first 26 weeks and last 26 weeks.
 51 Questionnaires will be evaluated at all time points they are collected.

52 **6 Description of Statistical Methods**

53 **6.1 Analysis Cohorts**

- 54 • All subjects enrolled in the study who initiate the CGM and have at least 168 hours of
 55 CGM data will be included in the tabulations of demographics and the glycemic
 56 outcome measures listed in Section 5
- 57 • CGM use assessment will include all subjects who stayed in the study at least one week
 58 following CGM initiation.
- 59 • HbA1c, questionnaires, insulin, and other analyses will include all subjects with any
 60 amount of corresponding data following CGM initiation.
- 61 • The tabulations of the safety outcomes will include all participants who enrolled,
 62 regardless of how much data is available.

63 **7 Analysis of Study Endpoints**

64 **7.1 Calculation of CGM Metrics**

65 **7.1.1 Calculation of 13 Week CGM Metrics**

66 All CGM metrics listed in Section 5 will be calculated on a 13-week period for each subject
 67 level. The windows for the 13-week periods are defined as follows:

Time Point	Window
1-13 Weeks	0 to 91 days after the CGM initiation date
14-26 Weeks	92 to 183 days after the CGM initiation date
27-39 Weeks	184 to 274 days after the CGM initiation date
40-52 Weeks	275 to 365 days after the CGM initiation date

68
 69 For each 13-week period, CGM metrics will be calculated by pooling all CGM readings
 70 occurring from 12:00 AM on the first day of the 13-week period up until 11:59PM on the last
 71 day of the 13-week period. For the first 13-week period, the first CGM reading will be the start
 72 datetime of the period. If a participant discontinues CGM prior to the last day of the 13-week
 73 period, then CGM data will include readings up to the last CGM reading on the discontinuation
 74 date. Calibrations will be excluded from all these calculations. CGM metrics for 13-week periods
 75 with less than 168 hours of CGM data will be set to missing.

76 Baseline CGM metrics will be calculated by pooling all blinded CGM readings up to 90 days
77 prior to the date of CGM initiation for each subject. Baseline CGM metrics with less than 72
78 hours of CGM data will be set to missing.

79 The amount of time using the CGM will be calculated as the number of CGM values multiplied
80 by the expected CGM measurement frequency (i.e., 5min in general), with the exception that
81 there can only be one value within the CGM measurement frequency. Percentage of time CGM
82 is used will be calculated as the amount of time using the CGM divided by the total possible time
83 the participant could have used the CGM during the same period. Note that this denominator
84 includes sensor warm-up periods with no CGM values, so this metric will serve as a conservative
85 estimate of CGM use.

86 **7.1.2 Calculation of 4 Week CGM Metrics**

87 All CGM metrics listed in Section 5 also will be calculated on a 4-week interval for each subject.

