112 document, with the ethical principles that have their origin in the Declaration of Helsinki, with  
113 the protocol described herein, and with the standards of Good Clinical Practice (GCP).

114 **Chapter 2: Study Enrollment and Baseline Data Collection**

115 **2.1 Participant Recruitment and Informed Consent**

116 Adults (age  $\geq 18$  years) with type 1 diabetes or type 2 diabetes using insulin therapy (Tidepool-  
117 compatible pump or injections) will be enrolled. Although the primary focus of the study is to  
118 enroll non-CGM users, CGM users whose glycemic control is suboptimal can be enrolled.  
119 Participation will be limited to U.S. residents in states where the virtual clinic is licensed; state  
120 eligibility will be verified as part of screening. Potential participants may be recruited through  
121 insurance providers, primary care networks, or health care providers. Potential participants also  
122 may become aware of the study by other means, such as another study participant.

123 Up to 800 individuals may sign the informed consent form to initiate screening. Enrollment will  
124 proceed with the goal of at least 300 participants initiating training for CGM use with the Virtual  
125 Clinic. The goal will be to limit T2D enrollment to no more than 100. Recruitment efforts will be  
126 focused on participants who receive diabetes care in a primary care setting rather than through an  
127 endocrinologist, with a goal of having at least 225 who have not seen an endocrinologist in the  
128 past six months. Eligible participants will be included without regard to gender, race, or  
129 ethnicity.

130 The goal will be to include at least 50 participants  $<25$  years of age and at least 50 participants  
131  $>65$  years of age.

132 **2.1.1 Informed Consent and Authorization Procedures**

133 Individuals who indicate that they are interested will be directed to a website with information  
134 about the study. Interested individuals will be able to communicate with study staff who can  
135 answer questions about the study as part of the informed consent process. Individuals who want  
136 to participate in the study will sign the Institutional Review Board (IRB) approved electronic  
137 consent form. As part of the informed consent process, each participant will be asked to sign an  
138 authorization for release of personal information. Participants will be asked to sign an addendum  

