212 Other sensors that become FDA approved during the course of the study may be included as an  
213 option for participants. If additional sensors are included, the participants will be given  
214 information about CGM system options and will review the CGM systems with a study team  
215 member. A recommendation may be provided for one of the systems based on discussion with  
216 the participant, or there may be an indication that there is no specific recommendation.  
217 Participants will be able to select the CGM system that they prefer, regardless of  
218 recommendation. After a CGM system is selected, the participant may be asked why that system  
219 was selected.

220 **2.7 Blinded CGM**

221 Non-CGM users will use a blinded CGM device for a single sensor wear period (usually at least  
222 10 days) prior to CGM initiation. Current CGM users will be asked to use a blinded CGM device  
223 for a single sensor wear period if their current CGM data cannot be successfully shared to  
224 confirm eligibility. Study supplies required for blinded CGM data collection will be sent to the  
225 participant by mail. An Android phone may be provided which is used as a receiver to collect  
226 data from the blinded Dexcom G6 Pro. Current non-Dexcom CGM users, including pump users  
227 with integrated CGM should continue to use their personal CGM for glucose management.

228 A virtual clinic team member will be available to answer questions about blinded CGM use. The  
229 participants will not be able to see the glucose values and will be expected to follow their normal  
230 diabetes management practice during this blinded CGM use period. The goal will be to obtain  
231 ten days of blinded data. Participants may be asked to use a blinded CGM for an additional  
232 sensor wear period if enough CGM data are not available to establish baseline comparator data.  
233 Participants will be dropped from the study if blinded data cannot be obtained. Participants who  
234 have a serious skin reaction to the sensor during blinded CGM wear that precludes continued use  
235 of a sensor will be dropped. If additional FDA-approved CGM options are available for use in  
236 this study, the participant may be offered the opportunity to try the other CGM system; in this  
237 case blinded data collection would be repeated with another system.

238 **2.8 Psychosocial Screening Questionnaires**

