#### 445      Safety Outcomes: Severe Hypoglycemia and DKA events, and hospitalizations

### 447      **6.4 Description of Statistical Methods**

#### 448      **6.4.1 Analysis Cohorts**

449      All subjects enrolled in the study who initiate the CGM and have a minimum amount of data as  
450      defined in the SAP will be included in the tabulations of baseline and the efficacy analyses. All  
451      subjects enrolled in this study will be included in the safety analyses.

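### Feasibility of introducing CGM remotely is a stated aim, but no planned outcome gives the proportion who initiate, and the CGM-use result leaves out first-week leavers and very low users

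*SAP*

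**What the plan says.** **Aim.** The SAP title describes the trial as "A Study Evaluating Remote Initiation of Continuous Glucose Monitoring". The précis in SAP Table 1 begins: "This study will assess feasibility and efficacy of establishing a virtual diabetes clinic with a focus on introduction of CGM technology".

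**Outcomes.** Protocol 6.3 and SAP 5 cover HbA1c, CGM glucose metrics, CGM use (in the SAP, percentage of time and hours), insulin, questionnaires and service utilization. SAP 5 adds a percentage of CGM discontinuations and a discontinuation survey. Neither list has a proportion completing baseline, starting CGM or completing the training sessions.

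**Cohorts.** SAP 6.1 sets these populations:
- Glycemic outcomes and demographics: "All subjects enrolled in the study who initiate the CGM and have at least 168 hours of" CGM data.
- CGM use: "CGM use assessment will include all subjects who stayed in the study at least one week" after initiation.
- HbA1c, questionnaires, insulin and other analyses: subjects with any "amount of corresponding data following CGM initiation".
- Safety: everyone enrolled, although SAP 8 tabulates the named safety events and person-years only from CGM initiation.

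Protocol 6.4.1 frames the efficacy population in the same way: "All subjects enrolled in the study who initiate the CGM and have a minimum amount of data as" set by the SAP.

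**Before initiation.** Protocol 2.4 to 2.7 require questionnaires, a mailed HbA1c sample and, for non-CGM users, a period of blinded sensor wear. Current CGM users wear the blinded sensor only if their own data cannot be shared. On the blinded phase, Protocol 2.7 says: "Participants will be dropped from the study if blinded data cannot be obtained". Protocol 5.5 allows withdrawal of people who are slow to complete baseline.

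**Recruitment.** Protocol 2.1 allows up to 800 consents, with a goal of at least 300 starting CGM training. Protocol 6.2 and SAP 4 call this a convenience sample.

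**Tracking.** SAP 9, on adherence and retention, specifies only contacts with the virtual clinic. SAP 10 confines the baseline table to initiators in the glycemic analyses. SAP 11 lists participant status and dropouts with reasons, but only for ongoing monitoring.

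**The concern.** A study of remote initiation should be able to say how many of the people who set out to start CGM did start. This plan measures what happens to those who started. Most of them have already managed a mailed sensor at home, because the blinded phase requires it of non-users. The use analysis then requires them to have stayed a further week, and the missing-data rule can remove those who hardly wore the device.

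What is at stake is the feasibility conclusion. If the plan is followed exactly, the report can describe CGM use among people who got going and stayed, but it has no pre-specified estimate of how many of the eligible got that far. A high use figure could then be taken as evidence that remote initiation works for the eligible population, which it would not show.

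**Working it through.** The plan gives no feasibility figure to reproduce, and 300 is not the result of a calculation. The check is of denominators, followed by some bounding arithmetic.

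**1. Where each result starts.** All three non-safety cohorts in SAP 6.1, and the efficacy cohort in Protocol 6.4.1, are conditional on initiation or on data collected after it. A participant who enrols, is eligible and never starts CGM is therefore in no pre-specified efficacy or use result.

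**2. What reaching 300 shows.** Inputs: 300 initiators (goal) and 800 consents (ceiling), both from Protocol 2.1.
- With exactly 300 initiators, the proportion of consenters who initiate could be anything from 300/800 = 37.5% to 300/300 = 100%.
- The 800 includes people found ineligible at screening, so 37.5% is a floor and not an estimate.

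**3. Initiation rate among the eligible.** The documents do not give the eligible number E, so E is assumed. Rate = 300/E, with exact (Clopper-Pearson) 95% intervals:

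| Assumed E | 300/E | 95% CI |
|---|---|---|
| 400 | 75.0% | 70.5 to 79.2 |
| 500 | 60.0% | 55.6 to 64.3 |
| 600 | 50.0% | 45.9 to 54.1 |

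These rows show how differently the same 300 could be interpreted, and that the rate would be estimated to within about 4 to 5 percentage points once E is known.

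**4. The one-week condition.** It concerns staying in the study, not wearing the sensor. It can still remove people who stop CGM in the first week, because Protocol 3.1 follows participants only until they discontinue CGM.

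**5. The 168-hour rule.** SAP 7.1 applies to all CGM metrics in SAP 5, and that list includes percentage of time using CGM. Share of a window below which the value becomes missing = 168/(days × 24):
- First 13-week window, days 0 to 91 (92 days): 168/2208 = 7.6%.
- First 26 weeks, days 0 to 183 (184 days): 168/4416 = 3.8%.
- A 28-day window such as days 29 to 56: 168/672 = 25.0%.

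On this reading, the lowest users become missing values instead of low values.

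**6. How the two rules interact.** Seven full days contain 7 × 24 = 168 hours, and SAP 7.1.1 notes that sensor warm-up produces no readings. Anyone who leaves within the week therefore has under 168 hours. Removing the one-week condition alone would leave their percentage of time missing.

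**7. Discontinuations.** The percentage in SAP 5, also tabulated by subgroup in SAP 12, is not tied to the one-week rule. If it belongs to the other analyses in SAP 6.1, a day-3 stopper can count. If it is part of the CGM use assessment, that person may not. The SAP does not say which applies.

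**The case against.** The strongest reply has five parts.

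- **Early failures are not invisible.** The discontinuation percentage and survey can capture people who start and stop, withdrawal reasons are collected (Protocol 5.5), and SAP 11 tracks dropouts. This stands. A reader might infer that failures of remote initiation cannot appear anywhere in the results, and the documents do not support that. What is missing is a denominator for discontinuation and any outcome for those who never start.
- **Run-in loss is not failed initiation.** Blinded wear and the mailed HbA1c sample serve the research baseline, and a precluding skin reaction is an exclusion criterion. An undivided all-enrolled denominator would mix research burden with feasibility of the clinic. This stands, and the fix separates them.
- **The literal aim is the clinic model.** The précis speaks of establishing a virtual clinic, and Protocol 1.1 reports a completed study that showed virtual initiation could succeed. This is partly right. But the same sentence of the précis puts the focus on introducing CGM, the title names remote initiation, and an earlier study does not supply this study's initiation rate.
- **SAP 6.1 sets no hours threshold for CGM use.** This may mean the 168-hour rule was intended only for glycemic metrics. That is possible, but SAP 7.1 makes no such exception.
- **Everything is exploratory, with no primary outcome, and the table shells are separate.** The shells may hold a participant-flow table. That limits the seriousness of the point, but a flow table is not a defined feasibility outcome.

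**Conclusion.** The concern holds in this form: the feasibility aim has no matching initiation outcome, all efficacy and use cohorts start after initiation, and the use result is narrowed further by the one-week condition and, on a literal reading, by the 168-hour rule. This limits what can be concluded about feasibility. It is not an error in a confirmatory test.

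The 7.6% cut-off follows from the SAP's own window. The 75%, 60% and 50% initiation rates rest entirely on assumed eligible numbers and predict nothing.

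A reader might also infer that the plan overstates continued use by a calculable amount. The documents do not support that. They measure use as time and hours per participant, define no proportion still using CGM at a given week, and give neither the first-week loss nor the number eligible.

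**What to change.** 1. **SAP 5 and 9.** Add the number and proportion, with 95% CI, of eligible enrolled participants who complete baseline, initiate CGM, and complete Trainings 2 and 3. Give reasons for loss at each step. Show ineligibility (including precluding skin reactions) and failure of research run-in procedures separately from failure to initiate.
2. **SAP 5 and 6.1.** Define the discontinuation percentage on all initiators. Add the proportion still using CGM at 13 and 26 weeks on the same denominator, with early leavers counted as discontinued.
3. **SAP 6.1 and 7.1.** For percentage of time using CGM, remove the one-week condition and do not apply the 168-hour missing rule; keep that rule for glycemic metrics. At the least, report this all-initiator analysis beside the planned one. State whether time after stopping stays in the denominator, since SAP 7.1.1 ends a discontinuer's data at the stopping date.

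The cost is SAP wording and one table, built largely from status data already monitored under SAP 11. The use figure is likely to become somewhat less favourable.
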